- If  $\leq 1$  of 6 subjects in a dose cohort experiences a DLT, then 6 subjects will be enrolled at the next higher dose level. Dose escalation will continue until a dose level is reached where  $\geq 2$  subjects experience a DLT, or when 750 mg is reached based on

an integrated evaluation of safety, tolerability, clinical benefit, PK, and pharmacodynamic data, for all dose levels tested.

[figure not shown]
Additional enrollment (if necessary)

If needed for selection of RP2D, an additional 3 subjects may be enrolled at 1 or 2 selected dose levels.

Panel A: Overall Dose Escalation Schema

Panel B: First Dose Cohort (Staggered dosing)

ssIR = suspected severe immune reaction

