## 9.5.5 Safety Assessments

Safety assessments will consist of monitoring and recording all AEs, including all CTCAE grades (for both increasing and decreasing severity), and serious adverse events (SAEs); regular laboratory evaluation for hematology, blood chemistry, and urine values; and periodic measurement of vital signs, echocardiograms/MUGA scans, electrocardiograms (ECGs), and physical examinations as detailed in [Table 6](#). The effects of E7046 on cardiovascular repolarization will be evaluated via continuous Holter/ECG monitoring. Subjects with decreasing hemoglobin levels or gastrointestinal symptoms indicative of gastrointestinal bleed should be evaluated for a potential gastrointestinal bleeding source as appropriate.

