### **Assessing Severity of Adverse Events**

Adverse events will be graded on a 5-point scale according to CTCAE v4.03 ([Appendix 4](#)). Investigators will report all CTCAE grades for AEs.

The criteria for assessing severity are different than those used for seriousness ([Section 9.5.5.2](#) for the definition of an SAE).

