5.6.3 Adverse Events

The adverse event verbatim descriptions (investigator terms from the eCRF) will be classified into standardized medical terminology using the Medical Dictionary for Regulatory Activities (MedDRA) version 18.0 or later. Adverse events will be coded to primary System Organ Class (SOC) and preferred term (PT) using MedDRA.

A treatment-emergent AE (TEAE) is defined as an AE that emerged during treatment (from first dose to 30 days after last dose of study drug) and

- had been absent at pretreatment (Baseline) or
- reemerged during treatment, having been present at pretreatment (Baseline) but stopped before treatment, or
- worsened in severity during treatment relative to the pretreatment state, when the AE was continuous.

Only those AEs that are treatment emergent will be included in summary tables. All AEs, treatment emergent or otherwise, will be presented in subject data listings.

The incidence of TEAEs will be reported as the number (percentage) of subjects with TEAEs within SOC and PT. Subjects will be counted only once within a SOC and PT, even if the subject experienced more than one TEAE within a specific SOC and PT, and the subject will be counted with the worst grade for that particular AE. The number (percentage) of subjects with TEAEs will also be summarized by highest Common Terminology Criteria for Adverse Events (CTCAE) grade. The number (percentage) of subjects with treatment-related TEAEs will also be summarized by SOC and PT. Treatment-related TEAEs include those events considered by the investigator to be possibly or probably related to study treatment. In summary, the following TEAE tables will be provided:

- Overview of TEAEs
- TEAEs by SOC and PT
- TEAEs by SOC, PT, and CTCAE grade
- TEAEs with CTCAE grade 3 or 4 by SOC and PT
- TEAEs that led to drug discontinuation by SOC and PT
- TEAEs that led to dose reduction by SOC and PT
- TEAEs that led to dose interruption by SOC and PT
- Treatment-related TEAEs by SOC and PT
- Treatment-related TEAEs with CTCAE grade 3 or 4 by SOC and PT
- Treatment-emergent serious AEs by SOC and PT
- Treatment-related treatment-emergent serious AEs by SOC and PT

Subjects AE listings (treatment emergent or not) will be provided. In addition, the following subject AE listings will be provided:

- All fatal adverse events.
- All non-fatal serious adverse events (SAEs)
- All non-fatal non-serious treatment-emergent adverse events that led to discontinuation of treatment

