13.4 Common Terminology Criteria for Adverse Events (v4.03)

The National Cancer Institute's *Common Terminology Criteria for Adverse Events* (CTCAE v4.03 published 28 May 2009; v4.03: June 14, 2010) provides descriptive terminology to be used for AE reporting in clinical trials. A brief definition is provided to clarify the meaning of each AE term. To increase the accuracy of AE reporting, all AE terms in CTCAE version 4.03 have been correlated with single-concept, Medical Dictionary for Regulatory Activities (MedDRA®) terms.

CTCAE v4.03 grading refers to the severity of the AE. CTCAE Grades 1 through 5, with unique clinical descriptions of severity for each AE, are based on this general guideline:

Table 5 Common Terminology Criteria for Adverse Events v4.03 Grading

| Grade | Status |
|-------|---|
| 1 | Mild: asymptomatic or mild symptoms; clinical or diagnostic observations only; intervention not indicated. |
| 2 | Moderate: minimal, local, or noninvasive intervention indicated; limiting age-appropriate instrumental activities of daily living (ADL). ^a |
| 3 | Severe or medically significant but not immediately life-threatening: hospitalization or prolongation of hospitalization indicated; disabling, limiting self-care ADL. ^b |
| 4 | Life-threatening consequences: urgent intervention indicated. |
| 5 | Death related to adverse event. |

a: Instrumental ADL refers to preparing meals, shopping for groceries or clothes, using the telephone, managing money, etc.

b: Self-care ADL refers to bathing, dressing and undressing, feeding self, using the toilet, taking medications, and not bedridden.

Source: Cancer Therapy Evaluation Program, NCI. CTCAE v4.03. Available from:

http://evs.nci.nih.gov/ftp1/CTCAE/CTCAE_4.03_2010-06-14_QuickReference_5x7.pdf.

For further details regarding MedDRA, refer to the MedDRA website:
<http://www.meddramsso.com>.

CTCAE v4.03 is available online:

http://evs.nci.nih.gov/ftp1/CTCAE/CTCAE_4.03_2010-06-14_QuickReference_5x7.pdf.

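### The severe-event tables in SAP 5.6.3 stop at Grade 4 and SAP 5.6.4 has no worst-grade laboratory shift: two cheap improvements to the by-dose safety summary

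*SAP*

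**What the plan says.** **Adverse events.** Protocol 9.5.5.1 sets the scale: "Adverse events will be graded on a 5-point scale according to CTCAE v4.03". SAP 13.4 defines the top grade: "Death related to adverse event". SAP 5.6.3 counts a subject once per SOC and PT, and "the subject will be counted with the worst grade for that particular AE". It lists 11 TEAE tables. Two are restricted to Grades 3 and 4: one for all causes, and "Treatment-related TEAEs with CTCAE grade 3 or 4 by SOC and PT". One table shows every grade, but for all causes only. The other related tables are related TEAEs by SOC and PT, and "Treatment-related treatment-emergent serious AEs by SOC and PT"; neither is listed as broken down by grade. Fatal events are also listed by subject.

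**Laboratory values.** SAP 5.6.4 plans by-visit descriptive statistics, change from baseline, and 3-by-3 low/normal/high (LNH) shift tables at each post-baseline visit. It defines an on-treatment window that closes 30 days after the last dose, but lists no summary of the worst value within it. SAP 8 confines by-visit analyses to scheduled visits.

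Safety and tolerability is a primary endpoint (Protocol 9.7.1.1, SAP 5.1.1) and is summarized by dose level (Protocol 9.7.1.6).

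**The concern.** Readers of a dose-finding report look for the number of subjects per dose with a related event of Grade 3 or higher. The table closest to that count leaves out the most severe grade. If a related event is fatal, its row loses the subject, and the dose looks slightly safer there than it was.

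The laboratory tables have a similar gap. Under Protocol 9.3.1, subjects may enter with ALT, AST or alkaline phosphatase up to 3 × ULN (5 × ULN with liver metastases), total bilirubin up to 1.5 × ULN, or creatinine below 1.5 × ULN. The criteria also allow exceptions or alternative routes for bilirubin, alkaline phosphatase and creatinine. A subject who starts above ULN and rises further is high at baseline and high afterwards, so the LNH shift does not move.

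**Working it through.** **Denominators.** The plan's sizes reproduce: 4 cohorts × 6 = 24 in escalation; 24 + 6 = 30 and 24 + 16 = 40 in total. Protocol 9.1.1.1 also says "an additional 3 subjects may be enrolled at 1 or 2 selected dose levels", so a cohort can reach 6 + 3 = 9.

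**Counting rule applied to one related term, cohort of 6.** Suppose the worst grades are 5, 3, 2, none, none, none. The Grade 3–4 row counts 1/6 = 16.7%. Grade 3 or higher is 2/6 = 33.3%.

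**Size per related death.** The term's row falls by 1/n. A total across terms falls by at most 1/n, and by nothing if the same subject keeps another related Grade 3 or 4 term.

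| Group | n | 1/n, percentage points |
|---|---|---|
| Escalation cohort | 6 | 16.7 |
| Cohort with 3 added | 9 | 11.1 |
| Expansion cohort alone | 6 to 16 | 16.7 to 6.25 |
| RP2D pooled, 6 + 6 to 6 + 16 | 12 to 22 | 8.3 to 4.5 |
| RP2D pooled, 9 + 16 | 25 | 4.0 |

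Pooling escalation and expansion subjects is an assumption; the documents do not state it.

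**How often it could arise.** The documents give no fatal-event rate. For an assumed per-subject related Grade 5 rate p, the chance of at least one is 1 − (1 − p)^n. For p = 1%, 2%, 5% and 10%:

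- n = 6: 5.9%, 11.4%, 26.5%, 46.9%
- n = 40: 33.1%, 55.4%, 87.1%, 98.5%

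**Laboratory illustration (assumed values).** Six subjects enter at ALT 3 × ULN and have three scheduled visits. In case A, one subject is at 10 × ULN at all three visits. In case B, three subjects are each at 10 × ULN at one different visit. All other values stay at 3 × ULN, and none of the rises is reported as an AE.

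- At every visit, both cases have the values 10, 3, 3, 3, 3, 3: mean 25/6 = 4.17, SD 2.86, Q1 = median = Q3 = 3, minimum 3, maximum 10.
- Mean change is 7/6 = 1.17 and maximum change is 7. The LNH shift is high-to-high in 6/6.
- Subjects ever reaching 10 × ULN: 1/6 = 16.7% in A, 3/6 = 50.0% in B.

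The by-visit tables are identical, although the number of affected subjects differs threefold.

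**Gaps between visits.** By Protocol Table 6, scheduled chemistry is 14 days apart from Day 8 to the next Day 1 in Cycles 2 to 6 (Day 8 to Day 22), and 21 days apart from Cycle 7. Unscheduled values drawn in between do not enter the by-visit tables.

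**The case against.** The case on the other side is substantial, and most of it stands.

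- **The tables are labelled correctly.** They say Grade 3 or 4 and do not claim to be the total severe rate. Protocol 9.7.1.10.2 asks for maximum severity and for relationship, not for the two crossed, so the SAP already goes further. What remains is that no listed related table supplies the Grade 3-or-higher count.
- **Table content is partly unknown.** The overview table's content is not stated, and the shells are a separate document (SAP 11). They may already cover part of this.
- **The SAP meets the protocol on laboratory data.** Protocol 9.7.1.10.3 asks only for values and changes by visit. Protocol 9.5.5.1 makes an abnormality an AE if it leads to an intervention or to withholding or withdrawing the drug. Such events appear in the AE table by grade. If the rises in the illustration were AEs, that table would separate the two cases. By-visit maxima and flagged listings help as well.

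A reader might also infer three stronger points, which the documents do not support.

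- **That deaths are hidden or dose decisions distorted.** Related deaths appear in the related table, the related-serious table and the fatal listing. DLTs are judged subject by subject after Cycle 1 (SAP 5.6.2), not from these tables.
- **That the SAP must state whether grade filtering or worst-grade selection comes first.** For a Grade 3-or-higher count, either order gives the same number.
- **That related events would be misclassified.** SAP 5.6.3 says "Treatment-related TEAEs include those events considered by the investigator to be possibly or probably related to study treatment", whereas the CRF question is Yes/No. Yes is the only recorded answer that can feed these tables, so the expected numerical effect is nil. The three-level wording in SAP 13.3 matches the protocol's DLT text.

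**Conclusion.** Both points hold as cheap improvements, not as errors that change a decision.

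Under the worst-grade rule, a Grade 5 event leaves its row in both severe-event tables. For all causes, the table by grade makes this good. For related events nothing listed does, and the reader must add the death back by hand. The cost is at most 16.7 percentage points per related death in a cohort of 6, down to 4.0 points in a pooled group of 25. It is zero if no related fatal TEAE occurs.

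The laboratory summaries cannot say how many subjects per dose worsened, or to what grade, when the abnormality was not reported as an AE. The illustration shows that this can happen but does not estimate how often. Both conclusions rest on the SAP text alone; the table shells and programming specifications were not available.

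**What to change.** 1. **SAP 5.6.3.** Change both severe-event tables to CTCAE Grade 3 or higher, by SOC and PT, with Grade 5 shown separately according to the subject's worst grade. No statement on the order of steps is needed for the Grade 3-or-higher count. Cost: SAP text and two table shells.
2. **SAP 5.6.4.** For CTCAE-gradable parameters, add shift tables by dose group from baseline grade to worst on-treatment grade. Use scheduled and unscheduled values up to the SAP's own limit of 30 days after the last dose, and keep the LNH tables for the other parameters. Cost: modest programming. The local reference ranges are already needed for the LNH classification.

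Neither change needs a protocol amendment or new subject data. Leave the DLT wording in SAP 13.3 as it is unless the protocol's DLT text changes with it.

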5.6.4 Laboratory Values

Laboratory results will be summarized using the *Système international* (SI) units. Abnormal laboratory values will be identified as those outside the normal range. The abnormal values will be indicated in data listings.

On-treatment laboratory tests are defined as laboratory tests conducted from the start of treatment to no more than 30 days after the last dose of study treatment. Descriptive statistics for laboratory test results as well as change from baseline at each visit will be produced by visit and dose group.

Only laboratory parameters specified in the protocol will be summarized. Other laboratory parameters collected for some individual subjects will be presented in listings only.

Laboratory test results will be assigned a low/normal/high (LNH) classification according to whether the value was below (L), within (N), or above (H) the laboratory parameter's reference range. Within-treatment comparisons for each laboratory parameter will be based on 3-by-3 tables (shift tables) that compare the baseline LNH classification to the LNH classification at each post-baseline visit.

5.6.5 Vital Signs

Descriptive statistics for vital signs parameters (diastolic and systolic blood pressure, pulse rate, respiratory rate, and body temperature) and changes from baseline will be presented by dose group for each cycle and visit.

5.6.6 Electrocardiograms

The 12-lead ECG assessments were performed at specific visits (screening, baseline, Day 1 of each treatment cycle and off-treatment visit) as described in the protocol. Shift tables will present changes from baseline in ECG interpretation (categorized as normal; abnormal, not clinically significant; and abnormal, clinically significant) by visit and dose group.

The left ventricular ejection fraction (LVEF) from MUGA or Echocardiogram will be evaluated at baseline (Screening) and off-treatment visit. Descriptive statistics for changes and % change at off-treatment visit from baseline will be presented by dose group for each cycle.

Continuous Holter/ECGs will be collected during Cycle 1 on Day 1 and Day 8 at predose, and 0.5, 1, 2, 4, 6, 8 and 10 hours post dose. The analysis of continuous Holter/ECGs results will be included in a separate plan and therefore excluded in this plan.

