### 9.7.1.10 Safety Analyses

Evaluation of safety will be performed on the Safety Analysis Set. Safety data to be evaluated include AEs, clinical laboratory results, vital signs, ECGs, and the results of physical examinations.

Safety assessments will consist of monitoring and recording all AEs and SAEs, using CTCAE version 4.03; regular laboratory evaluation for hematology, blood chemistry, and urine values; and regular performance of physical examinations, periodic measurement of vital signs, ECGs, and MUGA scans at baseline and as clinically indicated.

Safety parameters will be summarized using descriptive statistics (mean, standard deviation, median, Q1, Q3, and range for continuous variables; numbers and percentages for categorical measures).

The effects of E7046 on cardiovascular repolarization will be evaluated via 12-hour, 12-lead continuous Holter/ECG monitoring during Cycle 1 Day 1 and Day 8 in the Dose Escalation part of the study only. Individual ECGs will be extracted in replicate from the Holter recordings at specified time points and will be evaluated by a central laboratory. QT intervals will be measured from Lead II and will be corrected for QTc using Fridericia's (QTcF) correction factors. The primary QTc parameter will be QTcF. Secondary parameters (heart rate, PR and QRS) and T wave morphology will be evaluated. Potential effects of E7046 will be evaluated as change-from predose baseline heart rate, PR, QRS and QTcF by post-dosing timepoint. For purposes of QT assessment, exposure response analysis will be performed of the relationship between E7046 plasma levels and  $\Delta$ QTcF.

Safety ECGs will be analyzed using descriptive statistics for ECG parameters and changes from baseline will be presented by treatment cohort abnormal readings will be identified as those outside (above or below) the reference range. ECG findings will be summarized.

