#### 9.7.1.10.4 VITAL SIGNS

Descriptive statistics for vital signs parameters (ie, diastolic and systolic BP, pulse, respiratory rate, temperature, weight and changes from baseline will be presented by day and time after dosing and treatment cohort.

**MUGA Scans:** MUGA scans and/or echocardiograms will be assessed locally to determine LVEF. Summary statistics (standard deviation, median, and range) for LVEF changes from baseline will be calculated and summarized.

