5.6.7 Other Safety Analyses

No other safety analyses are planned for this study.

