8 DEFINITIONS AND CONVENTIONS FOR DATA HANDLING

Baseline Value is defined as a Day 1 pre-dose, or the last observation before the start of drug, if the Day 1 pre-dose is missing.

All by-visit analyses will be performed using assessments at corresponding scheduled visits recorded in the eCRF.

Partial dates for laboratory values, vital signs, and electrocardiograms (ECGs) will not be imputed.

Details on calculating pharmacokinetics parameters and the method to handle below limit of quantification (BLQ) values will be detailed in a separate plan.

When developing individual concentration-time profiles, BLQ values will be replaced with zero for the linear plot or missing for the semi-logarithm plot, respectively.

When calculating the mean or median value for the concentration at a given time point, the BLQ values will be assigned as zero. If the proportion of values reported as BLQ is more than 50%, no summary statistics should be represented at that time point, and the value will be treated as missing in mean or median concentration profiles.

More specific details, if any, are given with the discussion of analyses for each endpoint.

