- f. MUGA scans or echocardiograms will be performed at Screening, during the Off-Treatment Visit (window of ± 1 week), and if clinically indicated. MUGA scans and echocardiograms will be performed locally in accordance with the institution's standard practice.
- g. A serum pregnancy test (β -hCG) will be performed at screening for all premenopausal women and postmenopausal women who have been amenorrheic for less than 12 months. A urine pregnancy test will be performed at baseline before the first E7046 dose, and on Day 1 of every Cycle.
- h. 12-Lead ECGs will be collected at the following time points: Screening (single) and Baseline (single unless abnormalities are observed or if clinically indicated, then in triplicate at 2-minute intervals); Day 1 of all cycles (before and after study drug administration); and at the Off-Treatment Visit. In case of any alteration, or if clinically necessary, an echocardiogram and/or cardiac enzymes should be performed.
- i. Continuous Holter/ECGs (12-h/12-lead) to be collected during Cycle 1 on Day 1 and Day 8 at predose (3 timepoints within 45 minutes), and 0.5, 1, 2, 4, 6, 8, and 12 h postdose. At each of these timepoints, patients should be supinely resting for at least 10 minutes prior to and 5 minutes after the nominal time. When coinciding, blood draws, vital signs and 12-lead safety ECGs should be performed immediately after the timewindow for ECG extraction..
- j. Hematology and blood chemistry samples will be obtained before drug administration. Screening assessments may be used as baseline assessments if performed within 72 hours of the first dose of study medication. Before drug administration on Cycle 1, Days 1 and 8, a complete blood count should be drawn.
- k. Urine samples will be obtained before drug administration (either formal urinalysis or urine dipstick for protein and glucose are acceptable).
- l. Genomic DNA samples will be collected predose at baseline. If it cannot be collected at the designated time point, it may be collected at a time point after baseline.
- m. In Cycle 1, Day 1 and Day 8 All urine excreted will be collected as follows: pre-dose (0 hr), post-dose to 6hr, 6 to 12hr, 12-24hr. Total urine volume collected in each time interval will be recorded.Urine will be analyze for PK (E7046, M1 metabolite) and PD (PGE-M, metabolite of PGE2).
- n. Blood samples for PK analysis will be collected in Cycle 1 on Days 1 and 8 at predose (0 h), 0.5, 1, 2, 4, 6, 8, 10, and 24h postdose.

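### The SAP's LVEF summary uses only the Off-Treatment scan, so clinically indicated scans done during dosing are left out of it

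*SAP*

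**What the plan says.** **Collection.** Protocol 9.5.5.7 and footnote f of the schedule (protocol Table 6, SAP 13.1) place LVEF scans, by MUGA or echocardiogram, at Screening and at the Off-Treatment Visit, with further scans if there is a clinical reason. Footnote h sets 12-lead ECGs on Day 1 of every cycle and adds: "In case of any alteration, or if clinically necessary, an echocardiogram and/or cardiac enzymes should be performed".

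**Analysis in the protocol.** Section 9.7.1.10.4, in its paragraph on MUGA scans, states: "Summary statistics (standard deviation, median, and range) for LVEF changes from baseline will be calculated and summarized". It names no visit.

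**Analysis in the SAP.** Section 5.6.6 states: "The left ventricular ejection fraction (LVEF) from MUGA or Echocardiogram will be evaluated at baseline (Screening) and off-treatment visit". The next sentence gives the summary: "Descriptive statistics for changes and % change at off-treatment visit from baseline will be presented by dose group for each cycle". Section 8 adds a general rule: "All by-visit analyses will be performed using assessments at corresponding scheduled visits recorded in the eCRF". Section 5.6.7 closes the safety analyses: "No other safety analyses are planned for this study". Section 7 declares no change from the protocol's planned analysis.

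**The concern.** The protocol allows LVEF to be measured during dosing when something prompts it, but the SAP's LVEF summary has no place for the result. A scan done for cause is prompted by a possible cardiac problem, so the value left out may be the more informative one. The safety and tolerability profile is a primary endpoint (protocol 9.7.1.1), and protocol 9.7.1.6 has safety parameters summarised by dose level.

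The same SAP section handles ECG findings differently. "Shift tables will present changes from baseline in ECG interpretation", and these are tabulated by visit and dose group. An abnormal on-treatment ECG would therefore be tabulated, while the LVEF from an echocardiogram that it prompted would not.

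The summary sentence also cannot be programmed as written, because it asks for an off-treatment change for each cycle.

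**Working it through.** No alpha, power or rate is involved. The check counts the scheduled scans and then follows an unscheduled scan through the SAP's rules.

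1. **Scheduled scans per subject** (protocol 9.5.5.7; footnote f). Screening 1 + Off-Treatment 1 = 2. Post-baseline: 2 − 1 = 1. Tied to a treatment cycle: 0.
2. **Status of a scan during dosing.** Since no cycle has a scheduled LVEF scan, any scan between the first dose and the Off-Treatment Visit is unscheduled.
3. **Route through the SAP.** Section 5.6.6 names two LVEF time points, Screening and off-treatment, and summarises change at the second only. Section 8 would keep an unscheduled scan out of any by-visit table. Section 5.6.7 plans nothing further. The list of safety variables in SAP 5.6 does not name LVEF, so no general sentence brings the value back.
4. **The per-cycle wording.** With 0 scheduled scans in any cycle, a by-cycle LVEF table would have no scheduled data.
5. **Comparison with the protocol.** Section 9.7.1.10.4 asks for the standard deviation, median and range of LVEF changes from baseline without restricting the visit. The SAP restricts it to one.
6. **Other outputs that could show a fall.** Protocol 9.5.5.1 counts as an adverse event any unfavourable and unintended sign. It also counts deterioration in a clinical test not required by the protocol, if this leads to symptoms, a change in treatment or discontinuation. SAP 5.6 presents safety data by dose group, and SAP 5.6.3 tabulates TEAEs by CTCAE grade and by whether they led to reduction, interruption or discontinuation.

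Putting these together:

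| Subject's course | In the planned LVEF summary? | Elsewhere? |
|---|---|---|
| No unscheduled scan | Yes; a worst-value summary would give the same result | Not needed |
| Fall seen during dosing and still present at the Off-Treatment scan | Off-Treatment value only | TEAE tables if judged an AE |
| Fall seen during dosing, recovered by the Off-Treatment scan | The fall is not shown | TEAE tables if judged an AE |
| Fall seen during dosing, no Off-Treatment scan | No post-baseline value | TEAE tables if judged an AE |

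The loss is mainly in the last two rows, when the fall is not reported as an adverse event.

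**The case against.** **No protocol requirement is breached.** Section 9.7.1.10.4 does not demand a worst value or the use of unscheduled scans. Choosing the one scheduled post-baseline scan is a normal SAP decision, and leaving for-cause values to AE tables and listings is a common convention. This stands: the SAP is narrower than the protocol but does not contradict it. A reader might take protocol 9.7.1.10, with its "periodic measurement of vital signs, ECGs, and MUGA scans at baseline and as clinically indicated", as a commitment to analyse clinically indicated scans. That sentence describes what is monitored and recorded, not what is tabulated.

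**Footnote h does not guarantee scans.** A reader might infer that every ECG alteration produces an echocardiogram. The footnote is satisfied by cardiac enzymes alone, so neither the number of scheduled ECGs nor the number of dosing days before the Off-Treatment scan measures the gap.

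**Important falls have other routes.** A reader might infer that on-treatment LVEF falls go unreported. The documents do not support that. Besides the TEAE tables, a drug-related nonhematologic event of Grade 3 or higher in Cycle 1 is in general a DLT (protocol 9.1.1.2), and drug-related toxicity from Grade 2 upward triggers the actions in Table 2. The TLG shells are a separate document (SAP 11), so an LVEF listing cannot be ruled out. These routes narrow the gap. They do not close it, because AE tables depend on a reporting judgement and do not show measured LVEF by dose group.

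**The Off-Treatment scan is not uninformative.** The visit falls within 30 days of the last dose, so its scan can reflect the end of exposure. Protocol 7.1.3.3 anticipates low cardiovascular risk. Both are fair reasons for rating the point low.

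**A worst value has its own bias.** For-cause scans are selective, and a subject's lowest value tends to fall as scans accumulate. In cohorts of 6 with unequal time on treatment, differences between doses would partly reflect scan frequency. This stands, and it limits how the added table may be read.

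**Conclusion.** The point holds as a minor one. As written, the SAP leaves any clinically indicated LVEF scan done during dosing out of the dose-group LVEF summary, and its per-cycle wording cannot be carried out.

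The size of the gap cannot be estimated. The documents give neither the number of unscheduled scans nor the likelihood or depth of an LVEF fall, and if no unscheduled scans are done the summary loses nothing. The conclusion assumes that SAP 5.6.6 and 8 are applied as worded and that the separate TLG shells add no wider LVEF summary.

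A reader might go further and infer that the RP2D could be affected. The documents do not support that: the RP2D rests on an integrated evaluation (protocol 9.1.1.4), and toxicities judged to be adverse events reach that evaluation whatever the LVEF table contains.

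**What to change.** In SAP 5.6.6:

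- Delete the closing per-cycle phrase from the LVEF sentence and keep the Off-Treatment summary.
- Add, by dose group, each subject's lowest post-baseline LVEF and largest fall from baseline over all scheduled and unscheduled scans from first dose through the Off-Treatment scan. Give n, median and range, with the number of scans per subject alongside.
- Add a listing of all LVEF values.

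In SAP 8, state that the scheduled-visit rule does not apply to this summary.

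The cost is two wording edits, one short table and one listing, with no new assessments. The team must first confirm that the eCRF captures unscheduled scans, which the documents do not state. Because for-cause scans are selective, label the added table as descriptive and do not use it to compare doses.
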